Is WALANT Applicable in Distal Radius Fracture Osteosynthesis?

Study Protocol and Statistical Analysis Plan

October 2020

NCT (still not available)

ABSTRACT

Title → Is WALANT Applicable in Distal Radius Fracture Osteosynthesis?

Aims → To evaluate is Wide Awake Local Anaesthesia No Tourniquet (WALANT) is applicable to distal radius fracture (DRF) osteosynthesis and possible benefits of not using the ischemia cuff in distal radius osteosynthesis, by using the WALANT anaesthetic technique and compare it with patients who have undergone the current anaesthesia method (locoregional anaesthesia with or without sedation)

Material and methods → Randomized controlled study comparing patients operated on for distal radius fracture with osteosynthesis during a year (December 2020 to December 2021). The randomization will be done by 10 block in order to ensure similar numbers of patients in both groups of intervention. In the group A patients will be operated on with local anaesthesia (lidocaïne + adrenaline + bicarbonate) with or without sedation without the use of ischemia, while in group B patients will be given anaesthesia by proximal locoregional blockade with or without sedation and ischemia cuff. Immediate short-term results will be compared between both groups. Primary outcomes will be preoperative and postoperative pain, pre and postoperative swelling, and patient and surgeon satisfaction.

Results →

Conclusion →

1. INTRODUCTION

In recent years, the use of the WALANT (Wide Awake Local Anaesthesia No Tourniquet) anaesthesia technique is gaining weight, as multiple benefits of this type of anaesthesia have been found. The WALANT technique involves injecting local anaesthetic (lidocaine) at low doses and adrenaline to create a bloodless surgical field by avoiding the use of an ischemic tourniquet. In addition, there are many studies that support the safety of using this type of anaesthesia if it is administered according to the correct guidelines and dosage. (1), (2). Also, this technique has been shown to have high patient satisfaction rates. (3), (4)

Currently, and more so after Covid-19, which is causing unprecedented demand for an already saturated global health system, this anaesthesia technique is being implemented around the world in multiple centres and hospitals to perform some of the most common procedures in hand or foot surgery. Several studies can be found in the literature that demonstrate the benefits of applying circuits with anaesthesia type without the need for preoperative or admission compared to conventional Major Ambulatory Circuits (5), (6), (7).

The most commonly used drug for local anaesthesia is lidocaine, as it is the prototype short-acting anaesthetic and its physicochemical properties (solubility, relative potency, onset of action and duration) are those indicated to perform this type of procedure. The injection of lidocaine may or may not be associated with adrenaline, which produces vasoconstriction, decreasing local bleeding in the area, and at the same time prolongs the action of lidocaine. This combination of drugs can extend the duration of anaesthesia up to 3 hours. That is why in the WALANT technique these two drugs are administered together. Lidocaine is administered with a 1% (10mg / ml) solution, and if larger volumes or lower doses of anaesthesia are required, 0.5 of the solution may be used to avoid the maximum toxic doses, which in the combination of adrenaline + lidocaine, the maximum toxic dose is 7mg / kg with a maximum total dose of 500mg (50ml of 1% Lidocaine or 10cc of 5% Lidocaine). Concentrations above 1% lidocaine are not used, as they have not been shown to improve induction or duration of anaesthesia and may increase the risk of toxicity. In order to counteract the acidic pH of lidocaine, it is buffered with 8.4% (1M) sodium bicarbonate in a 10: 1 ratio, thus reducing pain during administration. This type of anaesthesia is performed according to the Lalonde's technique and is administered according to the Ahmad technique. (10) (22) (23) (24)

Our hypothesis is that the application of this anaesthetic technique, combined or not with sedation, causes less swelling and pain in the immediate postoperative period, without compromising patient satisfaction, altering short-term results or increasing the number of complications and without increasing the technical difficulty of the procedure to the surgeon.

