2.1. PRIMARY OUTCOMES

1. Pain (Difference between preoperative and postoperative EVA (24 hours, 10-15 days after surgery, 1 month after surgery))
 - a. Analgesia intake
2. Swelling (difference with healthy limb and difference between preoperative and postoperative (24 hours, 10-15 days after surgery, 1 month after surgery))
3. Patient satisfaction (Scale 1-5 and questionnaire)

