2.2. SECONDARY OUTCOMES

1. Evolution of the surgical wound (active bleeding and dressing condition at 24 hours and 10-15 days after surgery)
2. Postoperative mobility
 - a. Thumb mobility and opposition (Kapandji scale)
 - b. Finger mobility (capability of the patient to arrive at proximal and distal palm crease)
 - c. Wrist mobility (flexion, extension, pronation, supination, ulnar deviation, radial deviation)
3. Surgeon's technical difficulty.
 - a. Scale 1-5 (1 easy- 5 difficult)
 - b. Intraoperative stress /yes/no) and reason
4. Insufficient anaesthesia
 - a. Need of change to General Anaesthesia
 - b. Need of adding more anaesthesia
 - i. Type of anaesthesia used (sedation, local anaesthesia reinforcement, etc.)

- ii. Reason for change
- 5. Postoperative complications (total number and description)

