3.6 STATISTICAL PLAN

Quantitative values will be described as mean and standard deviation in case of normal distribution, or with median and interquartile range otherwise. Qualitative variables will be described with absolute and relative frequencies. The Student's t test for normal quantitative variables and the non-parametric Mann-Whitney U test will be used to compare the two experimental groups. Pearson's chi-square test for expected frequencies above 5 and Fisher's exact test would be used to compare the distribution of qualitative variables between groups. Statistical program R [ref] will be used, applying a statistical significance level of 5%.

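### The hypothesis includes a 'not worse' part (satisfaction, complications, technical difficulty), but section 3.6 plans only tests of zero difference, with no confidence interval, margin or rule for a non-significant result

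*Combined protocol and SAP*

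**What the plan says.** The hypothesis closes section 1 (Introduction) and has two parts. The first is that WALANT gives less swelling and pain soon after surgery. The second is that it does so "without compromising patient satisfaction, altering short-term results or increasing the number of complications" and "without increasing the technical difficulty of the procedure to the surgeon".

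The outcomes in the second part appear in section 2 as follows:

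- **Patient satisfaction** is primary (2.1): "Patient satisfaction (Scale 1-5 and questionnaire".
- **Technical difficulty** is secondary (2.2): "Scale 1-5 (1 easy- 5 difficult".
- **Complications** are secondary (2.2): "Postoperative complications (total number and description". Section 3.3 lists complications of anaesthesia and postoperative complications as separate items.

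Section 3.6 describes each group by mean and SD or median and IQR, and by frequencies for qualitative variables. For inference, Student's t or the "Mann-Whitney U test will be used to compare the two experimental groups", with Pearson's chi-square or Fisher's exact test for qualitative variables, all at 5%. Neither section 3.6 nor any other section mentions a confidence interval for a group difference, a non-inferiority or equivalence margin, or how a non-significant result will be interpreted.

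**The concern.** The planned tests suit the first part of the hypothesis: a significant reduction in pain or swelling would support it. The second part asks for something else, namely evidence that satisfaction is not lower and that complications and difficulty are not higher. A test of zero difference answers that only when it comes out significantly in favour of WALANT. Otherwise it reports that zero was not excluded, which fits no difference and may also fit a worthwhile loss.

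At stake is the second half of the hypothesis, including one primary outcome. It also bears on the main objective in section 2, which is to judge whether the technique is applicable as well as beneficial. The Limitations section warns that the sample may be small, so non-significant results on these outcomes are likely, and the plan gives the analyst no agreed way to read them.

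**Working it through.** **1. Hypothesis against method.**

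| Part of the hypothesis | What would support it | What section 3.6 provides |
|---|---|---|
| Less pain and swelling | A significant difference in favour of WALANT | Tests of zero difference: adequate |
| Satisfaction not compromised | An interval that excludes a stated loss | Test of zero difference and group summaries |
| Complications not increased | An interval that excludes a stated rise | Test of zero difference and frequencies |
| Difficulty not increased | An interval that excludes a stated rise | Test of zero difference and group summaries |

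The mismatch in the last three rows is one of logic and depends on no number.

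**2. Figures to reproduce.** There are none. The documents give no sample size, power, SD, event rate or margin. Everything below uses assumed inputs: 20, 40 or 60 per arm (equal arms, as the blocks of 10 intend), a satisfaction SD of 0.8 to 1.0, and invented complication counts.

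**3. Satisfaction, 1-5 scale.** The 95% half-width for a difference in means is t(0.975, 2n−2) × SD × √(2/n).

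- n = 20: 2.024 × 0.8 × 0.316 = 0.51; with SD 1.0, 0.64.
- n = 40: 1.991 × 0.8 × 0.224 = 0.36; with SD 1.0, 0.45.
- n = 60: 1.980 × 0.8 × 0.183 = 0.29; with SD 1.0, 0.36.

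So at 20 per arm, even an observed difference of exactly zero would be compatible with a true loss of half a point.

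**4. Complications, counted as patients with at least one.** This is an assumed endpoint; section 2.2 lists a total number. The Newcombe interval combines the Wilson limits (l, u) of the two arms: lower = d − √[(p1−l1)² + (u2−p2)²], upper = d + √[(u1−p1)² + (p2−l2)²].

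For 3/20 with WALANT against 1/20 with block, d = 0.15 − 0.05 = 0.10. The Wilson limits are 0.052 to 0.360 and 0.009 to 0.236.

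- Lower: 0.10 − √(0.098² + 0.186²) = −0.11.
- Upper: 0.10 + √(0.210² + 0.041²) = +0.31.

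| WALANT vs block | Smallest expected count | Test under the 3.6 rule | Risk difference (95% CI), points |
|---|---|---|---|
| 3/20 vs 1/20 | 2 | Fisher p = 0.60 | +10 (−11 to +31) |
| 6/40 vs 2/40 | 4 | Fisher p = 0.26 | +10 (−4 to +25) |
| 9/60 vs 3/60 | 6 | Chi-square p = 0.07 (0.13 with continuity correction) | +10 (−1 to +22) |

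All three tables are non-significant with three times as many affected patients under WALANT. With equal 5% rates, the interval is about ±19, ±12 and ±9 points at 20, 40 and 60 per arm. With no events in either arm it is ±16, ±9 and ±6.

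**5. What a non-significant t test does imply.** If p>0.05, the observed difference is smaller than the half-width, so the 95% limit lies within twice that value. At 60 per arm and SD 0.8 this is 2 × 0.289 = 0.58 points; at 20 per arm and SD 1.0 it is 2 × 0.640 = 1.28 points. A bound therefore exists once n and SD are known, but the plan neither reports it nor compares it with anything.

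**The case against.** The best defence has four strands.

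- **The plan reports more than p-values.** This stands. A reader might infer that p>0.05 sets no limit on harm, or that the plan would hide a difference. The documents do not support that: section 3.6 reports group means with SDs, or medians with IQRs, and counts with percentages. The observed difference would be visible, and an interval could be derived from means with SDs or from counts. What is missing is a stated interval and a rule for using it.
- **No misreading has been committed.** This also stands. A reader might infer that the sponsor means to treat p>0.05 as proof of no worsening, or has designed a non-inferiority trial. No section says either; the abstract says only "Immediate short-term results will be compared between both groups". The planned tests can also refute the second part by showing significant harm. But they give no route to supporting it short of a significant benefit, and the hypothesis asserts it.
- **The figures show low power, which the protocol partly discloses.** It is true that the sizes rest on assumptions, that the tables are chosen examples, and that the Limitations section admits a possibly small sample. The mismatch in step 1 of the working does not rest on them.
- **The complications example changes the endpoint.** This is right. A total number per patient could fall under the t or Mann-Whitney rule, so the proposed risk difference has to be declared as an addition.

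Three neighbouring matters should not be counted in support. 'Short-term results' is tied to no variable. The abstract lists "pre and postoperative swelling, and patient and surgeon satisfaction" among the primary outcomes, while section 2.2 places surgeon's difficulty among the secondary ones. Sections 2.2 and 3.3 word the difficulty item differently. These are outcome-definition questions and add no weight to a point about the choice of analysis.

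**Conclusion.** The concern holds in this form: the planned inference suits the superiority part of the hypothesis but, short of a significant benefit, cannot support the part saying that satisfaction, complications and technical difficulty are not worse. The plan has no interval, margin or reading rule to fill the gap. One primary outcome is affected. It would go too far to infer that the trial's main comparisons are undermined; the pain and swelling tests are unaffected.

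The logical point needs no assumptions. The size does: under the assumed inputs, the interval half-width for satisfaction runs from 0.64 points (20 per arm, SD 1.0) to 0.29 points (60 per arm, SD 0.8), and a threefold difference in complications stays non-significant in each table examined. This should be fixed, and the change is small.

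**What to change.** Keep the existing tests in section 3.6 and add text such as:

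> For patient satisfaction, surgeon's technical difficulty and complications, we will report the WALANT-minus-block difference with a two-sided 95% confidence interval: the mean difference for the 1-5 scales, and the risk difference for patients with at least one complication. The latter is an added summary beside the total number of complications. A p-value above 0.05 will not be read as 'not compromised' or 'no increase'. We will conclude 'not worse' on an outcome only if its interval excludes a margin fixed before any outcome data are seen; otherwise the outcome is descriptive.

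Two details go with it. State whether the anaesthesia complications in section 3.3 are counted with the postoperative ones. If no margins are set, soften the hypothesis in the Introduction so that it describes these outcomes instead of asserting that they are not worse. The mean difference is suggested even where Mann-Whitney is the test, because Hodges-Lehmann limits on a 1-5 scale move in whole points; this is a preference, not a requirement.

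The cost is SAP wording, a few intervals and early agreement on any margin. Conduct and data collection do not change. Surgeons score difficulty themselves during a year of recruitment, so waiting until the analysis to set a margin would be too late.

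The downside is that this part may be inconclusive in a small sample. From n = 2 × SD² × (1.96 + 0.84)² / margin² (80% power, one-sided 2.5%, true difference zero), a half-point margin needs 41 per arm with SD 0.8 and 63 with SD 1.0. Replacing SD² by p(1−p), a 10-point complication margin needs 75 per arm at a 5% rate and 142 at 10%. These margins, SDs and rates are assumptions for illustration. If such numbers are out of reach, reporting intervals with descriptive wording is the realistic choice.

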2. OUTCOMES OF THE STUDY

The main objective of this study is to assess the applicability and benefits of LANT (Local Anaesthesia No Tourniquet) anaesthesia versus locoregional anaesthesia with proximal block and ischemia in osteosynthesis of distal radius fractures postoperatively immediately.

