3.2. INCLUSION AND EXCLUSION CRITERIA

Inclusion criteria will be those patients ≥18 years of age who agree to participate.

Patients with any of the following conditions will be excluded from the study:

1. Do not sign informed consent.
2. They have associated fractures in which additional osteosynthesis is required: scaphoid fracture, ulnar fracture, bifocal radius fractures, etc.
3. Open fractures.
4. Polytrauma
5. Non-synthesized flying fractures with a single plate or other type of plate.
6. Patients in whom a different surgical technique than the one mentioned above has been required.
7. Contraindications to the use of ischemia (14)

- a. Peripheral vascular disease.
- b. Seriously injured or traumatized limb.
- c. Peripheral neuropathy or CNS disease
- d. Severe infection in the limb.
- e. Thromboembolic disease in the extremity.
- f. Poor skin condition of the limb.
- g. Arteriovenous fistula.
- h. Sickle cell hemoglobinopathy.

8. Contraindications for proximal blocking: (15)

- a. Existence of previous trauma or anatomical distortion of the area that prevents the abduction of the arm.

- b. Active presence of infection at the puncture site.
- c. Previous axillary lymphadenopathy.
- d. Previous history of local anaesthetic allergy.
- e. Severe coagulopathy.
- f. Severe pre-existing neurological diseases in the upper extremity.

9. Contraindications for WALANT anaesthetic technique

- a. Documented hypersensitivity to lidocaine.
- b. Compromised peripheral circulation.
- c. Patients with previous vascular pathology, a history of vasculitis, Buerger's disease, and scleroderma.
- d. Patients with infection of the area surrounding the injection.

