3.4. DATA COLLECTION AND INSTRUMENTS

A sample of patients with a distal radius fracture operated in our Hospital will be obtained. Those who meet the inclusion criteria will be asked to participate and will be told what the study is about. Those who accept must sign the specific informed consent of this study.

Prior to surgery, an external observer will collect the personal data of the patients, assign them a code (P1, P2, P3...) and perform the anamnesis following the Data Collection Guide Form

Patients' recruitment will be done during a year, from December 2020 to December 2021. They will be separated into two groups. The external observer will do this process with 10-block randomization using Study Randomizer (2017), a web based randomization service (19)

The first (Group A) in which WALANT technique will be performed and the second (Group B) in which locoregional anaesthesia (either axillary or supraclavicular block) with axillary ischemia will be applied. Because it is considered a long-term intervention, all patients will be offered the option of sedation or not, and this variable may change depending on the criteria of anaesthesia or the patient himself in order to facilitate their well-being. All patients participating in the study will receive the same antibiotic prophylaxis following our protocol (Cefazolin 1g iv in <80Kg or 2g 80-160Kg and in patients with normal renal function, to pass in 5 minutes. In those with FG The dose should be adjusted, and a second dose of 2g iv should be given if the surgery lasts 3 hours or more. In patients with penicillin allergy, Teicoplanin 600mg iv will be administered in 10 minutes, without repeating the dose. in no case) (20)

Group A (WALANT Anaesthesia +/- sedation + NO ischemia)

In WALANT technique, the doses are followed according to Lalonde's (21). 1% lidocaine with 1: 100,000 adrenaline is generally used to counteract the acidic pH of lidocaine, which is buffered with 8.4% (1M) sodium bicarbonate in a 10: 1 ratio to decrease pain during administration. If more volume is required, Lidocaine is diluted to 0.5% so as not to exceed the maximum toxic dose of 7mg / kg with a maximum total dose of 500mg (50ml of 1% Lidocaine or 10cc of 5% Lidocaine) (22)

In this case, the preparation will be made by the nurse with 100cc of SF, from which 15cc will be extracted and 10cc of 5% Lidocaine + 1cc Adrenaline + 4cc of 1M Bicarbonate will be added.

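### Applicability is the title question and half of the main objective, but it is undefined and rests on secondary outcomes with no interval or criterion for success

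*Combined protocol and SAP*

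**What the plan says.** The title asks "Is WALANT Applicable in Distal Radius Fracture Osteosynthesis", and the aim in the abstract repeats the question. Section 2 makes applicability one of two parts of the objective: "The main objective of this study is to assess the applicability and benefits of LANT (Local Anaesthesia No Tourniquet) anaesthesia versus locoregional anaesthesia".

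Section 2.1 lists three primary outcomes: change in pain, with analgesia intake; "Swelling (difference with healthy limb and difference between preoperative and postoperative"; and "Patient satisfaction (Scale 1-5 and questionnaire". The abstract names a further primary outcome, surgeon satisfaction, which section 2.1 does not list. In section 2.2 the surgeon's technical difficulty and stress are secondary.

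The items closest to applicability are all in section 2.2: item 3 (surgeon difficulty), item 4 (insufficient anaesthesia, including "Need of change to General Anaesthesia" and any added anaesthesia, with type and reason) and item 5 (complications). Section 3.6 describes qualitative variables by counts and percentages and compares groups by chi-square or Fisher tests at the 5% level. It mentions neither a confidence interval nor applicability. Section 3.5 (Limitations) accepts that the sample may be small, and no target number is given.

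**The concern.** A reader of the final report will expect an answer to the title. As planned, the primary results say how the two groups compare on pain, swelling and satisfaction. They do not say whether a distal radius plate can reliably be fixed under WALANT without changing the anaesthetic. The data that could say so are collected, but with three gaps:

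- **Definition.** Nothing says what counts as success. Sedation shows the problem. Sections 3.1 and 3.4 allow it in both groups as an option, while sections 2.2 and 3.3 list it as a response to insufficient anaesthesia. The same sedated patient could be counted either way.
- **Precision.** A percentage without an interval hides how little a small group can exclude.
- **Basis for the conclusion.** The only planned inference is a between-group test. With few events it will usually be non-significant, and that result is easily read as showing that the technique is applicable.

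**Working it through.** The documents give no sample size, expected failure rate or margin, so there is no stated figure to reproduce. All group sizes, event counts and rates below are assumptions. Only the two-group design, the roughly 1:1 allocation (blocks of 10) and the 5% level come from the plan; two-sided testing is assumed.

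**1. What zero failures would exclude.** With 0 failures in n patients, the upper limit of the exact (Clopper-Pearson) two-sided 95% interval is 1 − 0.025^(1/n).

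| Assumed n in group A | Upper limit for the true failure rate |
|---|---|
| 15 | 21.8% |
| 20 | 16.8% |
| 30 | 11.6% |
| 40 | 8.8% |
| 50 | 7.1% |

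For n = 30: 0.025^(1/30) = 0.884, and 1 − 0.884 = 0.116. With 2 failures in 30 (6.7%) the exact interval is 0.8% to 22.1%.

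**2. How the planned test can mislead.** Suppose 5 of 30 in group A are converted and 0 of 30 in group B. The expected count per group is 5 × 30/60 = 2.5, below 5, so section 3.6 leads to Fisher's test. The probability that all five fall in group A is C(30,5)/C(60,5) = 142,506/5,461,512 = 0.0261. The mirror-image table is equally likely, so the two-sided p = 0.052. This is not significant at 5%, yet the observed WALANT failure rate is 16.7%, with exact limits 5.6% and 34.7% (0.025 quantile of Beta(5, 26) and 0.975 quantile of Beta(6, 25)).

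**3. How often the test would detect a real difference.** The usual normal approximation for two proportions at 80% power is

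n per group = [1.96·√(2p̄(1−p̄)) + 0.842·√(p₁(1−p₁) + p₂(1−p₂))]² / (p₁−p₂)².

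- Failure 20% v 5% (p̄ = 0.125): (0.917 + 0.383)²/0.0225, about 76 per group. At 30 per group, power is about 42%.
- Failure 10% v 2% (p̄ = 0.06): (0.658 + 0.279)²/0.0064, about 138 per group. At 30 per group, power is about 25%.

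At such sizes a non-significant result is likely even when WALANT fails several times as often as the block.

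**4. Denominator.** For failure of the technique, the patients allocated to group A are the denominator, provided none is removed afterwards. Exclusion 6 in section 3.2 (a different surgical technique was required) may become known only at operation, so it could remove some.

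**The case against.** The strongest reply is that the plan measures applicability quite fully. Item 4 of section 2.2 is a single headed outcome covering conversion, reinforcement, type and reason. Section 3.3 adds extra WALANT doses and intraoperative pain where no sedation was needed. Three stronger readings are tempting, and the documents do not support them.

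- *The trial would yield no estimate of how often WALANT works.* Section 3.6 reports qualitative variables as absolute and relative frequencies, so the percentage converted or reinforced in group A is already planned. What is missing is the interval, the definition and a criterion.
- *All primary outcomes measure benefit only.* The hypothesis in the Introduction expects benefit in swelling and pain, but places satisfaction among the things not to be compromised. Section 3.3 asks whether the patient would repeat or recommend the anaesthesia, which bears on acceptability. The abstract's surgeon satisfaction also touches on applicability, though it conflicts with section 2.1 and has no cut-off.
- *Without a count of all screened fractures the question cannot be answered.* Section 3.4 says "A sample of patients with a distal radius fracture operated in our Hospital will be obtained", and section 3.2 excludes patients unsuited to the cuff, the block or WALANT. No screening log is described, but that is not evidence that none is kept. Section 2 sets applicability against locoregional anaesthesia and does not ask what share of all fractures suits WALANT. The log is needed only under that second meaning, and is otherwise a reporting matter.

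It is also fair to say that the wide intervals come from the missing sample size, and that promoting an outcome does not narrow them. That stands. The interval would at least make the imprecision visible, which the p-value does not.

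**Conclusion.** The point holds as one of ranking, definition and inference, not of missing data. The title and half of the main objective rest on secondary outcomes with no definition of success, no interval and no criterion, and section 2.1 contains no technique-success measure. The size depends on assumed numbers: with 20 to 50 patients in group A and no failures, true failure rates up to 16.8% to 7.1% remain compatible with the data, and 5 failures of 30 against none would still be non-significant. The comparison of pain, swelling and satisfaction is not affected by this point. It is worth correcting because the headline conclusion would otherwise lack a stated basis, and the correction is cheap.

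**What to change.** 1. **Define the estimate.** Use the proportion of all patients allocated to group A whose operation is completed as allocated, that is, without general anaesthesia, proximal block or ischaemia cuff. Show sedation and local reinforcement separately. Remove nobody after allocation, including under exclusion 6.
2. **Report it** with an exact 95% confidence interval as the key estimate for applicability. Base any statement on applicability on that interval, not on a between-group p-value.
3. **Set any threshold early.** If a minimum proportion is to be called applicable, fix it before the first patient. Conversions are seen in theatre as they occur, so database lock is too late. The threshold should also be attainable: 0 failures in 30 gives a lower limit for success of 100 − 11.6 = 88.4%, so 90% could not be shown at that size. Without a threshold, limit the objective and conclusion to benefits.
4. **Reconcile** the abstract and section 2.1 on surgeon satisfaction.
5. **Optional:** report a tally of screened and excluded patients by criterion. It is needed only if the sponsor means the share of all fractures suited to WALANT.

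Cost: one definition, built mainly on section 2.2 item 4. Section 3.3 lists ischaemia time for group B only, so a yes/no entry for cuff use in group A may have to be added to the form. No extra patients or visits are needed. The downside is one more headline estimate in a plan that already has several primary outcomes, and it may be imprecise. A preset threshold would also act as a decision rule and should be described as one.
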